## 9.5 ANALYSIS OF SAFETY

The safety analyses will be carried out in the safety population.

### 9.5.1 Tolerability parameters

Laboratory parameters will be summarized for each visit by means of descriptive statistics. Changes from baseline and 95% confidence interval on mean change will also be provided. Frequencies and percentages of low, normal and high values for each parameter at each time point will also be provided. Laboratory data will also be listed with clinically significant information.

Physical examinations will be summarized as frequency and percentages of normal and abnormal body system at each time point. Weight and BMI will be summarized by means of descriptive statistics and changes from baseline.

### 9.5.2 Adverse Events

Adverse events (AEs) intensity and frequency will be analysed during the pre-treatment phase and in the treatment phase until End of Study Visit.

The following summary tables will be provided:

- Adverse Events by SOC and PT;
- Serious Adverse Events by SOC and PT;

- Drug related Adverse Events by SOC and PT;
- Pre-Treatment Adverse Events by SOC and PT;
- Serious Pre-Treatment Adverse Events by SOC and PT;
- Treatment-Emergent Adverse Events by SOC and PT;
- Serious Treatment-Emergent Adverse Events by SOC and PT;
- Drug related Treatment-Emergent Adverse Events by SOC and PT;

Serious adverse events and fatal adverse events will also be listed.

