#### 5.4 Withdrawal of subjects

Participation may be discontinued for any of the following reasons:

---

 Checked by medical history

- voluntary subject withdrawal for any reason;
- at the Investigator's discretion (reason should be specified);
- if an adverse event (including worsening of concomitant illness) develops, which is considered by the Investigator as incompatible with the continuation of the study;
- if the administration of a drug which is not permitted according to the exclusion criteria is necessary (this should be discussed between the Investigator and the Sponsor);
- failure to comply with the requirements of the protocol or significant protocol deviation (e.g. inclusion error, evidence of non-compliance with exclusion/inclusion criteria arisen during the study, subject misses study visits or/and is not compliant with drugs intake, etc.);
- if a pregnancy develops;
- lost to follow-up;
- patient death;
- if LT4 dose adjustment is required upon receipt of baseline (V2) laboratory results and before any control visit (interim or unscheduled) is performed;
- if PPIs dose adjustment outside the allowed range is necessary or if PPIs are discontinued.

Subjects who withdraw or are withdrawn from the study after inclusion in the Tirosint® treatment phase (V2) will not be replaced. Subjects who withdraw or are withdrawn from the study before inclusion in the Tirosint® treatment phase (during the run-in phase) will be considered as screening failures.

See section 7.4 for the assessments to be performed in case of early withdrawal.

[figure not shown]

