## **10 ADVERSE EVENTS DESCRIPTION & REPORTING**

Adverse event definitions and classification are reported in [Appendix I](#).

All the occurred adverse events (AEs), independently from their classification, must be reported on the CRF in the “adverse event” section.

A dedicated form is required for the reporting of the Serious Adverse Events (SAE form).

All the Serious Adverse Events (SAE) which occur during the clinical trial, independently of their causal relationship, must be reported immediately (i.e. within 24 hours after first knowledge) by fax or email to:

The collection period of AEs/SAEs for each subject starts from the signature of the informed consent until the end of the study and/or the follow-up planned period.

When the Investigator has received knowledge of an SAE, he/she should fulfill a SAE form (Type of report: initial) with the support of the **Study Coordinator/Monitor**, if necessary, and send it to  by fax or email as soon as possible but within 24 hours.

The preliminary notification should include, at least, this minimum information:

- 1) EUDRACT (if applicable) and protocol numbers;
- 2) Patient’s identification (initials - only when applicable according to local regulations- screening/randomization number, date of birth, gender), relevant medical history;
- 3) SAE description and its onset;
- 4) Investigator’s causality assessment on the event relationship with the study medication;
- 5) IMP batch N°, first admin- and last admin before SAE, if code broken – when applicable;
- 6) Specific treatment of the SAE;
- 7) Investigator: name, address, phone number.

SAEs must be monitored until resolution or acceptable stabilization in the event of chronicity.

In case of death, the Investigator will be requested for forwarding the autopsy report, if available.

When the investigator receives additional information regarding the initial SAE, he/she should fill in a new SAE form and tick the “Follow Up” box and fax or email it within 48 hours to the .

All SAEs, qualified for the reporting to FDA, will be submitted to FDA by IBSA or its delegate according to the post-marketing pharmacovigilance reporting requirements, within **15 calendar days** from IBSA's first knowledge.

Follow-up reports will be reported within 15 calendar days of receipt of new information or as requested by FDA.

The clock for expedited reporting (day 0) starts as soon as the information containing the minimum reporting criteria has been received by IBSA.

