#### **Safety Analyses**

Numbers of patients experiencing Adverse Events (AEs) will be calculated. AEs will be classified using MedDRA categories. Vital signs and body weight will be analyzed by means

of descriptive statistics. Moreover mean change from baseline and 95% confidence interval on mean change will also be calculated.

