### **6.3 SAFETY POPULATION (SP)**

All included patients.

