## **9 STATISTICAL METHODOLOGY**

### **9.1 GENERAL METHODOLOGY**

#### Descriptive statistics

- Continuous variables will be summarized by mean, standard deviation, median, 1st quartile, 3rd quartile, minimum and maximum.
- Discrete variables will be summarized by frequencies and percentages.

All p-values will be rounded to four decimal places. Statistical significance will be declared if the two tailed p-value is less than 0.050.

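### Adverse events are tabulated for the pre-treatment and capsule phases without exposure time, so the two sets of figures are not comparable side by side

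*SAP*

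**What the plan says.** SAP 9.5.2 splits adverse events by phase: "Adverse events (AEs) intensity and frequency will be analysed during the pre-treatment phase and in the treatment phase until End of Study Visit". Among its listed tables are "Pre-Treatment Adverse Events by SOC and PT" and "Treatment-Emergent Adverse Events by SOC and PT", with a serious-event version of each. The section does not give the cell format, and SAP sections 13 and 14 contain no shells, so the format has to be taken from elsewhere. SAP 9.1 says "Discrete variables will be summarized by frequencies and percentages", and Protocol 11.3.6 says "Numbers of patients experiencing Adverse Events (AEs) will be calculated". Neither document mentions patient-time, an exposure-adjusted rate or equal time windows for adverse events.

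The phases differ in length. In both study schedules the run-in is 28 to 42 days and the final visit falls at day 84, with a window of 77 to 91. Protocol 7.2 (Re-screenings) lets the whole screening period run to 4 months.

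Three further statements fix which events and patients are counted:
- Protocol 10: "The collection period of AEs/SAEs for each subject starts from the signature of the informed consent".
- SAP 6.3 defines the safety population as "All included patients". Inclusion takes place at Visit 2, and Protocol 5.4 treats those who leave earlier as screening failures.
- SAP section 5 counts a pre-treatment event only if it began after inclusion and before the first dose.

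**The concern.** The trial has a single arm, so the run-in is the only period on tablets in which adverse events are recorded. A reader of a safety report with a pre-treatment table and a treatment-emergent table, laid out alike by system organ class and preferred term, will naturally compare them. The longer phase collects more events, and more patients with at least one event, even if the switch changes nothing. A difference caused by the calendar could then be taken for an effect of the capsules. Percentages do not remove this, because the share of patients with at least one event also grows with time.

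The definition in SAP section 5 adds a second difficulty. The schedule puts inclusion at Visit 2, and the first capsule should be taken that day. Read literally, the pre-treatment window is close to zero. An event in the run-in would then be neither pre-treatment nor treatment-emergent, and could appear only in the tables that are not split by phase. If inclusion is read loosely as enrolment, the window is the whole run-in. A rate cannot be formed until it is clear which window applies.

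**Working it through.** The documents give no adverse event rate, so there is no plan figure to reproduce. The check asks what the planned tables would show if the rate were the same in both phases.

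**Inputs from the documents**
- Run-in of 28 to 42 days; midpoint 35 days (5 weeks) used as the central case.
- Capsule phase of 84 days (12 weeks), window 77 to 91.
- Longest pre-treatment period 4 months = 4 × 30.4375 = about 122 days, or 17.4 weeks.
- 47 patients included (SAP 4.1), taken here as fully followed.

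**Assumed:** the share p of patients with at least one event in the run-in, varied from 5% to 30%.

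**Events, nobody re-screened.** Expected ratio = capsule days / run-in days.
- Central: 84/35 = 2.4
- Lowest: 77/42 = 1.83
- Highest: 91/28 = 3.25

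**Patients with at least one event.** The 12-week share is 1 − (1 − p)^(12/5).

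| Run-in share, 5 weeks | Capsule share, 12 weeks | Ratio |
|---|---|---|
| 5% | 11.6% | 2.3 |
| 10% | 22.3% | 2.2 |
| 20% | 41.5% | 2.1 |
| 30% | 57.5% | 1.9 |

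At 20%, that is 47 × 0.20 = 9.4 patients against 47 × 0.415 = 19.5. Across the visit windows the second figure runs from 15.8 (6 versus 11 weeks) to 24.2 (4 versus 13 weeks). The ratio for patients is below the ratio for events and shrinks as events become more common.

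**Effect of re-screening.** If a share s of patients has L pre-treatment weeks and the rest have 5, the event ratio is 12 / [sL + (1 − s) × 5].
- s = 20%, L = 12: 12/6.4 = 1.88.
- One patient who uses the full 4 months: 84/122 = 0.69, so the direction reverses.
- The group ratio reaches 1.0 at L = 17.4 only if s = (12 − 5)/(17.4 − 5) = about 56%.

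The documents do not say how many patients were re-screened.

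**Effect of leaving out run-in failures (numbers assumed).** Take 47 included patients with a 20% share and 6 failures.
- Failures also at 20%: (9.4 + 1.2)/53 = 20.0%, unchanged.
- Failures at 50%: (9.4 + 3.0)/53 = 23.4%, against 20.0% with included patients only.

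**After the change.** At an assumed 0.05 events per patient-week, the run-in gives 47 × 5 × 0.05 = 11.75 events and the capsule phase 47 × 12 × 0.05 = 28.2. Dividing by 235 and 564 patient-weeks returns 0.05 in both, a ratio of 1.0.

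**The case against.** The strongest reply is that the plan never makes this comparison. SAP 9.5.2 lists descriptive tables with no test, difference or ratio between phases. Protocol section 4 names the baseline evaluation, not the run-in event count, as each patient's control. The phase lengths are printed in both schedules, so a careful reader can allow for them. This stands, and it limits the point to presentation. It does not remove it: the SAP chose to split the tables by phase, and in 9.5.4 it already scales compliance to the length of the period.

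A reader might also infer that leaving out patients who fail the run-in ("during the run-in phase) will be considered as screening failures") pushes the run-in figure down. The documents do not support that for percentages. These patients leave both numerator and denominator, and the percentage falls only if they had more events than the included patients. That is possible, since an adverse event can end participation, but no figure shows it. Using the same included patients in both phases is also the coherent basis for reading the two tables together. SAP 9.2 reports reasons for screening failure, so an event that stopped inclusion may still surface there.

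**Conclusion.** The point holds as a low-severity reporting improvement. Without exposure time, the pre-treatment and treatment-emergent tables cannot be read against each other. With a constant rate and no re-screening, the expected excess on capsules is about 2.4-fold in events (1.8 to 3.3) and about 1.9- to 2.3-fold in patients, for assumed run-in shares of 5% to 30%.

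A reader might go further and conclude that the tables must make the capsules look worse. The documents do not support that as a general statement. The size depends on the unknown share re-screened, and the direction can reverse for an individual patient. If the definition in SAP section 5 is applied literally, the pre-treatment table would be nearly empty and the contrast larger, but the wording leaves open whether that is intended. The efficacy analysis and sample size are not affected.

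**What to change.** In SAP 9.5.2, for the included patients, add total patient-time and events per patient-month in each phase beside the numbers and percentages of patients. State that the unadjusted figures of the two phases are not meant to be compared.

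In SAP section 5, define a pre-treatment adverse event as one starting from consent and before the first dose, and compute pre-treatment patient-time over the same interval. Consent may precede the screening visit (Protocol 7.2), and the reporting guidance in Protocol Appendix I gives the screening date as the start of collection. The SAP should therefore name one start point and use it for both events and time.

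Optionally, list the adverse events of run-in failures separately, without merging them into the phase tables.

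The rates need only consent, visit, first-dose and event dates. The cost is a few extra columns and slightly longer safety output. The optional listing may need additional data entry, because Protocol 11.1.2 commits to database storage for included subjects only.

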### 9.5.3 Vital signs

Vital signs (including heart rate, systolic and diastolic blood pressure) and body weight will be analyzed by means of descriptive statistics. Moreover mean change from baseline and 95% confidence interval on mean change will also be provided.

### 9.5.4 Other tolerability parameters

#### Treatment compliance

- Patients' compliance with Tirosint® and with the prescribed treatments (levothyroxine as per prescription during the run-in and PPI during the run-in and throughout the whole treatment period) will be assessed based on data reported in the Subject's Diary, calculating the percentage of medication taken in relation to the actual period of treatment (number of doses reported to be taken during the period / number of doses envisaged to be taken during the period x 100).
  - Number of doses reported to be taken during the period will be computed as number of days through the visits reported with dose taken = "Yes" in the Subject's Diary.
  - Number of doses envisaged to be taken during the period will be computed as number of days from the previous visit to the next one.

Patient who didn't fill in Subject's Diary for at least one visit will not be considered for this analysis and compliance will be considered not evaluable.

- Patients' compliance with Tirosint® will also be assessed on the Drug Administration, calculating the percentage of medication taken in relation to the recommended dose and the actual period of treatment (total amount of drug actually taken during the period / total amount of drug envisaged to be taken during the period x 100).

- Amount of drug actually taken will be computed from the drug accountability as sum of used amount of drug returned and used amount of drug not returned x related drug dosages.
- Amount of drug envisaged to be taken will be computed as prescribed dosage x period time.

Compliance will be defined as:

- *excellent* for consumption of study drug  $\geq 95\%$  of the amount envisaged.
- *good* for consumption  $\geq 90$  and  $< 95\%$ ;
- *poor* for values lower than 90%.

Compliance will be evaluated separately by visit.

Treatment compliance will be analyzed by means of descriptive statistics for:

- Tirosint® compliance from Subject Diary
- Tirosint® compliance by visit from Subject Diary
- LT4 compliance from Subject Diary
- LT4 compliance by visit from Subject Diary
- Tirosint® compliance from Drug accountability
- Tirosint® compliance by visit from Drug accountability
- PPI compliance from Subject Diary
- PPI compliance by visit from Subject Diary

Frequencies and percentages of patients' compliance classification (excellent, good or poor) will be provided for Tirosint® compliance from drug accountability data.

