### **Treatment compliance**

Patients compliance with Tirosint® and with the prescribed treatments (levothyroxine as per prescription during the run-in and PPI during the run-in and throughout the whole treatment period) will be assessed on the basis of data reported in the Subject's Diary, calculating the percentage of medication taken in relation to the recommended dose and the actual period of treatment (number of doses reported to be taken / number of doses envisaged x 100).

Patients compliance with Tirosint® will also be assessed on the basis of the number of units supplied and the units returned, calculating the percentage of medication taken in relation to the recommended dose and the actual period of treatment (number of doses actually taken / number of doses envisaged x 100).

Compliance will be defined as:

- *excellent* for consumption of study drug  $\geq 95\%$  of the amount envisaged;
- *good* for consumption  $\geq 90$  and  $< 95\%$ ;
- *poor* for values lower than 90%.

Compliance will be evaluated separately over run-in and treatment periods.

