### **6.6 PROTOCOL DEVIATIONS**

Any protocol violation or deviation (i.e., wrong inclusion, poor compliance, forbidden concomitant medications etc.) will be discussed by case before statistical analysis with the clinical team and described in the statistical report.

Violations will be classified as major violation or minor violation according to the impact on subject safety, the effect on completeness, accuracy and reliability of the data collected for the study, and the influence on the efficacy assessments. Protocol deviations related to COVID-19 will also be identified.

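### Read naturally, one missing diary removes a patient's complete diary periods too, while blank days count as missed doses; diary compliance for LT4 tablets and PPI can be biased in a direction the documents do not fix

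*SAP*

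**What the plan says.** SAP 9.5.4 (Treatment compliance) computes diary compliance as a ratio. The numerator is the "number of days through the visits reported with dose taken" marked Yes; the denominator is the "number of days from the previous visit to the next one". A patient who did not complete the diary "for at least one visit will not be considered for this analysis and compliance will be considered not evaluable".

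The time unit of the evaluation is set in three places. Protocol 11.3.6 states: "Compliance will be evaluated separately over run-in and treatment periods". SAP section 4, under the changes from the protocol, adds results by visit to make the evaluation more accurate. SAP 9.5.4 then lists by-visit diary tables for Tirosint, LT4 and PPI.

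Drug accountability gives a second compliance measure for Tirosint only. The *poor* class applies "for values lower than 90" percent, and the only class table planned is the "compliance classification (excellent, good or poor) will be provided for Tirosint® compliance from drug accountability data".

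SAP 6.6 gives, as examples of deviations to be discussed case by case before the analysis, "wrong inclusion, poor compliance, forbidden concomitant medications etc".

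**The concern.** The exclusion sentence is about the patient, whereas the compliance measure is defined per period and per visit. Applied as written, it removes usable data from the tables meant to show compliance by visit. It is also open to another reading (no diary for even one visit), so two programmers could produce different tables from it.

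The rule also treats missing information in two ways. A blank day in a returned diary scores zero; a diary that is wholly missing takes the patient out of the calculation.

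This matters most for run-in LT4 tablets and for PPI, which have no other quantified source. At the visits, PPI boxes are checked only for changes of product or dose, and only if the patient brings them. Each patient's own baseline on tablets is the control (Protocol section 4), so tablet intake before the switch and PPI intake throughout are conditions on which the before-after TSH comparison relies. A reader of the report will look to these tables to judge whether those conditions held.

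**Working it through.** The plan states no figure on this point that could be reproduced, so the check applies the SAP's own ratio and then a simple bias model.

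**1. What a patient-level exclusion discards.** Diaries cover three intervals: Visit 1 to 2 (28 to 42 days), Visit 2 to 3 (nominally 42 days) and Visit 3 to 4 (nominally 42 days). Suppose only the last diary is missing.
- Diary days that exist: 28 + 42 = 70, up to 42 + 42 = 84.
- Diary days in all: 28 + 84 = 112, up to 42 + 84 = 126.
- Complete data discarded: 70/112 = 62.5%, up to 84/126 = 66.7% of the patient's diary days, including the whole LT4-tablet record.

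Under the other reading (no diary at any visit) nothing usable is lost, because such a patient has no diary data.

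**2. How blank days score.** For a patient who took every dose, the smallest number of blanks that brings the ratio below 90% is:
- 3 of 28 days: 25/28 = 89.3%
- 5 of 42 days: 37/42 = 88.1%
- 9 of 84 days: 75/84 = 89.3%

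A few blanks therefore lower the figure, while an entirely missing diary yields no figure.

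**3. Net direction.** Let N = 47 (patients included in the treatment phase, SAP 4.1; the safety population is all included patients, SAP 6.3). Let k be the number excluded, c_r and c_n the true intake of the remaining and the excluded patients, and b the share of taken doses left blank by the remaining patients.
- Reported mean = c_r × (1 − b)
- True mean = [(N − k) × c_r + k × c_n] / N
- Reported exceeds true only if b < (k/N) × (1 − c_n/c_r)

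The documents give none of k, c_r, c_n or b; the values below are assumptions, with c_r = 97% throughout.

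Worked case, k = 5 and c_n = 80%: true mean = (42 × 97 + 5 × 80)/47 = 4474/47 = 95.2%. At b = 5% the reported mean is 97 × 0.95 = 92.15%, a difference of −3.0 points. Break-even b = (5/47) × (1 − 80/97) = 1.9%.

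Reported minus true, in percentage points:

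| k | c_n | b = 0% | b = 2% | b = 5% | break-even b |
|---|---|---|---|---|---|
| 5 | 80% | +1.8 | −0.1 | −3.0 | 1.9% |
| 5 | 50% | +5.0 | +3.1 | +0.1 | 5.2% |
| 2 | 80% | +0.7 | −1.2 | −4.1 | 0.75% |
| any | 97% | 0.0 | −1.94 | −4.85 | 0% |

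The sign changes within plausible inputs.

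**4. Worst-case bound.** Counting all days of a missing diary as not taken, with b = 0, gives (42 × 97)/47 = 86.7% for k = 5 and (45 × 97)/47 = 92.9% for k = 2. Each excluded patient is 1/47 = 2.1% of the denominator.

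**The case against.** Four things can be said for the plan, and most of them stand.

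- **The sentence may mean something milder.** The by-visit tables fit handling at period level, and the wording can also describe a patient with no diary for even one visit. That possibility is real. It argues for settling the wording, because the literal subject of the sentence is still the patient.
- **The SAP fills a gap.** The protocol has no missing-diary rule, and the SAP is meant to add detail, so the absence of this rule from the declared changes carries little weight. This stands.
- **Compliance is descriptive.** It does not enter the primary model, and the ITT and modified ITT sets do not depend on it. The per-protocol definition names no compliance threshold. This stands, and it limits the point to a minor one.
- **Period-level handling does not recover everything.** A patient without a run-in diary still has no LT4-tablet figure. This is true, and it is why a count of diaries not returned and a bound are needed as well.

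A reader might infer that non-returners can never be identified as poorly compliant. The documents do not support that. Capsule accountability still classes them for Tirosint, the deviation review considers poor compliance case by case, and sites check diaries for LT4 and PPI at Visits 2, 3 and 4. Nor do non-returners lose a tablet or PPI class that others receive, since that class is tabulated for no one. What they lack is a computed diary percentage.

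**Conclusion.** The point holds as a minor defect of wording and reporting. On its natural reading the rule discards complete diary periods, against the plan's own by-period and by-visit structure; on the other reading the effect is smaller. Missing diaries and blank days are scored by different rules, and for LT4 tablets and PPI no second quantified source shows the consequence.

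A reader might also infer that reported compliance is overstated. That is not established. Dropping patients raises the mean only if they took fewer doses than the others, which the documents do not say, and scoring blanks as missed lowers it. In the assumed cases above the net difference runs from +5.0 to −4.85 points. The supportable conclusion is that the figures can be biased in an unknown direction.

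The effect stays within a descriptive summary. It reaches efficacy only if poor compliance is judged a major violation and so decides per-protocol membership, in which case an affected patient would have no diary figure for tablets or PPI to inform that decision.

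**What to change.** In SAP 9.5.4:

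1. Make only the period whose diary is missing non-evaluable, and keep the patient's other periods.
2. Report n (%) with diary not returned, by product (Tirosint, LT4 tablets, PPI) and by period, out of the 47 included patients.
3. Add two sensitivity rows: one counting the days of a missing diary as not taken, labelled as a worst-case bound, and one leaving blank days out of the ratio.
4. List every missing diary for the deviation review under SAP 6.6, so that the per-protocol decision is taken with that information.

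The cost is a change of SAP wording and slightly more table work, with no new data. Reported compliance may look less favourable.
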